3.2 SCHEDULE OF ACTIVITIES

Below is a table detailing the key activities in intervention and control communities, from baseline through the end of the study.

Table 1. Detailed Overview of Activities by Control and Intervention Sites

	Planning	Baseline	3-month	6-month	9-month	12-month	15-month	
INTERVENTION AND CONTROL	 							
Pilot survey (phone or in-person) and qualitative interviews	Х							
Baseline BMU Census/ Registry verification & updating	Х	Х						
Eligibility screening and informed consent		Х						
Baseline survey		Х						
Social network mapping and randomization		Х						
Follow up survey – (includes HIVST self-report)			Х					
Qualitative in-depth interviews and focus group discussions (HIVST and network support)			x	х				
Linkage to ART or PrEP				х				
VL measurement and adherence for those initiating ART				х				
Urine tenofovir levels measurement and adherence for those initiating PrEP				х				
Qualitative in-depth interviews (Linkage and retention)				х				
INTERVENTION								
Enhanced training (HIV basics, HIVST, PrEP, and ART)		х	x	x				
HIVST for distribution via network-central promoters		Х	Х					
Voucher for cash redemption 500 KSH (at clinic linkage)		Х	Х					
Enhanced promoter support/training		Х	Х	х				
Retention support via SMS/phone			Х	х				
CONTROL	· ·							
Basic training (HIV basics and facility access/info)		х						
Voucher for HIV test or HIVST redemption at facility		Х	х					
Standard of care for ART or PrEP		Х	Х	х				

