5 OBJECTIVES AND ENDPOINTS

Table 2. Overview of Study Aims, Design, and Outcomes

	Study design and interventions	Outcomes
--	--------------------------------	----------

Aim 1	 Self-reported HIV testing within 3 months of intervention start BMU census / registry verification & updating Baseline social network data collection Identification of close social networks and network-central 'promoters' Baseline survey among those randomized to control and intervention RCT: Intervention: Promoters given training & multiple STs, & asked to offer STs to men in their social networks. Control: Promoters given basic training & vouchers for HIV testing (including HIVST) at clinics to offer to men in their networks 3-month follow-up survey Measure impact of intervention on linkage to & uptake of ART & PrEP Intervention: Promoters are given incentives (clinic transport reimbursement vouchers valued at ~\$5) & encouraged to give to men in their networks to promote linkage to ART or PrEP 	 Self-reported HIV testing uptake within 3 months Confirmatory HIV testing uptake 3 – 6 months after intervention start Linkage to ART or to PrEP within 3 months after self-reported HIV testing Initiation of ART or PrEP (among those eligible), within 3 months of confirmatory testing (linkage)
	 after HIV testing 2. Control: Promoters given same training & info, but no linkage incentives 	
Aim 3	 Measure impact of intervention on ART & PrEP retention & adherence Men who test HIV-positive undertake VL testing and counseling at scheduled intervals to ascertain adherence to ART Men who test HIV pagative 	 Viral suppression (HIV RNA <400 c/mL) and adherence at 6 & 12 months Adherence to PrEP (TFV levels of >=1500
	 Men who test HIV-negative undertake rapid HIV & TFV testing with counseling at scheduled intervals and urine testing to ascertain PrEP adherence 	ng/mL in urine = adequate adherence ²⁸) at 6 months
Qualitative	Across all aims, we will assess the path mixed methods quantitative and qualit	ways of intervention action using qualitative and ative assessment. We will identify the

Studies	mechanisms of action, and barriers and facilitators of the social network and incentives
	intervention implementation, using qualitative and mixed methods quantitative and
	qualitative assessments embedded in Aims 1, 2 and 3. The data collection approach will
	include in-depth interviews with participants in both groups, key informant interviews

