After the training, the intervention promoters will receive multiple HIV self-test kits for distribution to other men in their close social networks. The HIVST distribution will be as follows: each network-central promoter will receive a test kit for himself, and an addition number of kits (up to 8), for as many of his close network members as identified during the mapping exercise. They also will be given, and asked to distribute to men in their close social networks, transport vouchers for ART or PrEP after HIV self-testing. The voucher worth Ksh 500 (~\$5) will be used for reimbursement when seeking confirmatory testing for HIV and screening for ART or PrEP within 3 months of self-testing at home. The amount reflects prevailing transport and opportunity costs of time. In the session for promoters in the control group, the promoters will be given vouchers with information on facilities with free HIV testing and free self-tests at nearby health facilities, to distribute to men in their close social networks. The control promoters will receive a voucher with information about where to get an HIVST or standard HIV testing within the facilities in the community. The voucher will not have any monetary value. All promoters, in both groups, will be given up to Ksh 1000 (~\$10) for their participation in a full day of training.

Training curriculum is attached to this protocol.

8.6 3-MONTH FOLLOW UP SURVEYS/BASELINE FOR NEW PARTICIPANTS

Up to n=1500 participants

Visit 1 for new participants (those not mapped in the baseline but received self-tests with incentive vouchers (intervention) or referral vouchers (control) from promoters

Visit 3 for baseline mapped and surveyed participants who received self-tests with incentive vouchers (intervention) or referral vouchers (control) from promoters

Visit 4 for promoters who will have participated in the social network survey, baseline survey, and promoter trainings (visits 1 2 and 3, respectively)

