1.2 SAMPLE SIZE DETERMINATION AND POWER CALCULATIONS

Aim 1

We calculate that the study will have an 80% or greater power to detect a significant difference in the proportion of HIV testing associated with the intervention arm, assuming a proportion self-testing in the control arm of 38% (observed data from SEARCH in fishermen) if the proportion testing in the intervention arm is 52% or greater (odds ratio of 1.8), calculated using an Intraclass Correlation Coefficient (ICC) of 0.15 (conservative based on SEARCH data), 70 clusters each in the intervention and control arms, average cluster size of 7 in both arms, and a type-1 error rate of 5%.^{125,126} Figure 2 shows statistical power and the range of detectable odds ratios over extremes of clustering effects.

Aim 2

For the Aim 2 combined primary outcome of successful linkage to ART or PrEP within 3 months of intervention start (+about 1 month), this study will have a 80% or greater power to detect a significant increase in successful linkage, assuming a proportion successfully linked at 3 months in the control arm of 24% (based on observed SEARCH trial linkage rates weighted for the number of eligible PrEP HIV-negative men and HIV-positive men not currently in HIV care) if the observed proportion in the intervention arm is 39% or greater (odds ratio of 2.0), using an ICC of 0.15, 70 clusters each in intervention and control arms, a cluster size of 7 in both arms, and a type-1 error rate of 5%. Statistical power for combined ART or PrEP

start is similar, with a reduction in anticipated eligible numbers per cluster reduced to 6 resulting in a small increase in the detectable odds ratio to 2.2 or greater. Power for a separate analysis of ART initiation alone is likely to be low given the small numbers of new HIV infections in the study sample with odds ratios in excess of three or four required.

Aim 3

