1.3.3 ANALYSIS OF ADDITIONAL ENDPOINT(S)

Primary Outcome: the primary outcome measure will be linkage to care or prevention within 3 months of the Aim 1 intervention start. Linkage will be defined for HIV-positive participants as a documented confirmatory HIV test result, and a documented HIV clinic visit following referral. Linkage will be defined for HIV-negative participants as documented evidence of evaluation for PrEP (following standard of care procedures) extracted from medical records.

Secondary outcome: The secondary outcomes will be confirmatory HIV testing uptake 3 – 6 months after intervention start and the initiation of ART, or PrEP (among those screened as eligible), within 3 months of the confirmatory test or eligibility screening. HIV testing uptake will be measured via documented testing records in clinic records and ART start will be measured via documented prescription for ARV medications, and for PrEP start, via oral PrEP prescription.

Third outcome: The third primary outcome is a composite measure meant to capture "success" in HIV prevention and/or treatment behaviors. The measure will be defined as either adequate levels of tenofovir, indicating PrEP adherence (defined as TFV levels of >= 1500 ng/mL in urine indicating adequate adherence vs. < 1500 ng/ml) among HIV seronegative individuals who screened eligible for PrEP or the proportion of HIV-positive participants with viral suppression (defined as HIV RNA <400 c/mL using the Abbott realTime HIV-1 platform and assay, with a detectable threshold of 40 cells per microliter at 6 months. PrEP adherence will be measured at 6 months after initiation using our novel technology of point-of-care rapid testing to assess TFV adherence in urine (developed by Co-I [name] in collaboration with Alere Rapid Diagnostics[™]). For both components of the measure, we will define missing values as failure (i.e. inadequate adherence or unsuppressed).

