#### 11) Statistical Power:

**Aim 1:** We calculate that the study will have an 80% or greater power to detect a significant difference in the proportion of HIV self-testing associated with the intervention arm, assuming a proportion self-testing in the control arm of 38% (*observed data from SEARCH study in fishermen*) if the proportion testing in the intervention arm is 52% or greater (odds ratio of 1.8), calculated using an Intraclass Correlation Coefficient (ICC) of 0.15 (*conservative based on SEARCH data*), 40 clusters each in the intervention and control arms, average cluster size of 8 in both arms, and a type-1 error rate of 5%. Figure 2 shows statistical power and the range of detectable odds ratios over extremes of clustering effects.

**Aim 2:** For the Aim 2 combined primary outcome of successful linkage to ART or PrEP within 3 months of intervention start, defined as when the promotor receives the kits at the end of the promotor training which will be upon completion of the baseline survey for that beach. This study will have a 80% or greater power to detect a significant increase in successful linkage, assuming a proportion successfully linked at 3 months in the control arm of 24% (*based on observed SEARCH trial linkage rates weighted for the number of eligible PrEP HIV-negative men and HIV positive men not currently in HIV care*) if the observed proportion in the intervention arm is 39% or greater (odds ratio of 2.0), using an ICC of 0.15, 40 clusters each in intervention and control arms, a cluster size of 8 in both arms, and a type-1 error rate of 5%. Statistical power for combined ART or PrEP start is similar, with a reduction in anticipated eligible numbers per cluster reduced to 6 resulting in a small increase in the detectable odds ratio to 2.2 or greater. Power for a separate analysis of ART initiation alone is likely to be low given the small numbers of new HIV infections in the study sample with odds ratios in excess of 3 or 4 required.

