### 15) Timing of outcome assessments:

Research staff will collect data from all study participants in both arms at approximately 0 months/baseline, 3 months, 6 months, and 12 months. All assessments will have a window of +/- 1 month. Outcome assessments collected via clinical chart abstraction (HIV confirmatory testing and results, PreP screening and uptake, and ART screening and regimen, clinic attendance), survey (self-reported testing), and via specimen collection and analysis (HIV viral load testing and PreP adherence) will be assessed within one month of each participant's 6 or 12 month outcome window, through a study-scheduled visit.

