## Section 6: Analysis

# 26) Outcome definitions

- a. Primary Outcomes:
  - i. Proportion of HIV testing: The first primary outcome will be the proportion of study participants who self-report HIV testing in the last three months (at the 3 month follow up visit) compared to those who self-report not using testing during the last three months.
  - ii. Proportion of HIV self-testing: The second outcome will be the proportion of study participants who self-report using the self-testing kit in the last three months (at the 3 month follow up visit) compared to those who self-report not using a self-testing kit during the last three months.
  - iii. Proportion with successful linkage to ART or PrEP within 3 months of intervention start (ie: when promoters receive self-test kits to distribute). The second primary outcome will be defined as the proportion of individuals who link to ART (if confirmatory HIV testing is positive) or PrEP evaluation (if confirmatory HIV testing is negative), meaning they present at a study facility/clinic (depending on results of HIV testing) within three months of the intervention start (defined as from when study promotors receive the kits for distribution).
  - iv. HIV treatment and prevention success: The third primary outcome is a composite measure meant to capture "success" in HIV prevention and/or treatment behaviors (ie: Viral suppression among HIV+ and adequate TFV among those prescribed PrEP). The measure will be defined as either adequate levels of tenofovir, indicating PrEP adherence (defined as TFV levels of <1500 ng/mL in urine indicating inadequate adherence vs. ≥ 1500 ng/ml) among HIV seronegative individuals who screened eligible for PrEP *or* the proportion of HIV-positive participants with viral suppression (defined as HIV RNA <400 c/mL using the Abbott realTime HIV-1 platform and assay, with a detectable threshold of 40 cells per microlitre) at 6 and 12 months. Secondary thresholds of <1000 copies/mL will also be examined. PrEP adherence will be measured at 6 and 12 months after initiation using our novel technology of *point-of-care rapid testing to assess TFV adherence in urine* (developed by Co-I [name] in collaboration with Alere Rapid Diagnostics™). For both components of the measure, we will define missing values as failure (i.e. inadequate adherence or unsuppressed).

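### The Aim 2 primary linkage outcome is given three incompatible windows, one of which starts at self-reported testing and would break the intent-to-treat comparison

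*Protocol*

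**What the plan says.** Three rules for the same primary outcome appear in the current documents.

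- **Three months from intervention start.** Protocol Statistical Considerations 1.3.3 says that "the primary outcome measure will be linkage to care or prevention within 3 months of the Aim 1 intervention start", and its analytic plan repeats this. SAP section 26 requires the man to present at a study clinic "within three months of the intervention start (defined as from when study promotors receive the kits for distribution"; SAP section 11 gives the same time zero, "defined as when the promotor receives the kits at the end of the promotor training".
- **The same start, plus a month.** Protocol 1.2 powers the trial for "successful linkage to ART or PrEP within 3 months of intervention start (+about 1 month"). SAP section 15 states separately that "All assessments will have a window of +/- 1 month", without saying whether this moves the cut-off for the linkage event or only the date of data collection.
- **Three months from testing.** Protocol section 5, Table 2, lists "Linkage to ART or to PrEP within 3 months after self-reported HIV testing". Protocol Ethical Considerations 3.1 adds that Aim 2 linkage is measured for men in Aim 1 who report having used a self-test.

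The incentive has its own period. Protocol section 8.5 describes the Ksh 500 voucher, held only in the intervention arm, as reimbursement for "seeking confirmatory testing for HIV and screening for ART or PrEP within 3 months of self-testing at home". In Protocol Table 1, both the row "HIVST for distribution via network-central promoters" and the cash-voucher redemption row are marked at baseline and 3 months but not at 6 months. Linkage itself is marked only at 6 months.

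**The concern.** The rules classify different men as linked, and one of them changes who is compared. Whether a man tests is decided after randomisation, and raising testing is the whole of Aim 1. A linkage outcome that starts at testing, or is measured only in testers, compares two groups selected by the intervention.

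The restriction in section 3.1 to users of a self-test adds an imbalance. Under section 8.5, control vouchers point men to either a self-test or standard testing at a facility. A control man who takes the standard test and is evaluated for PrEP has linked by the 1.3.3 definition, but falls outside the group described in 3.1.

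The SAP's time zero also lacks a literal meaning in the control arm, because it is the receipt of kits and control promoters receive vouchers.

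**Working it through.** **1. The plan's own power figure.** Inputs are 24% against 39%, ICC 0.15 and two-sided 5% (Protocol 1.2; SAP sections 11 and 16). The effective number per arm is n = k·m / [1 + (m − 1)·ICC]. Power = Φ{[|p2 − p1| − 1.96·√(2·p̄·(1 − p̄)/n)] / √[(p1(1 − p1) + p2(1 − p2))/n]}, with p̄ = 0.315.

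- SAP, 40 networks of 8: n = 320/2.05 = 156.1; power 81.7%.
- Protocol, 70 networks of 7: n = 490/1.90 = 257.9; power 95.8%.

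The stated 80% or greater reproduces. Both documents describe 24% as the proportion linked at 3 months, so these figures already refer to a 3-month endpoint.

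**2. What conditioning on testing does.** Use the Aim 1 planning rates (38% control, 52% intervention) and assume, for illustration, that every linked man reported a test.

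| Case | Control | Intervention | Contrast |
|---|---|---|---|
| All randomised, planned effect | 24% | 39% | +15 points, OR 2.02 |
| Testers only, planned effect | 24/38 = 63.2% | 39/52 = 75.0% | +11.8 points, OR 1.75 |
| All randomised, no effect on linkage | 24% | 24% | 0 |
| Testers only, no effect on linkage | 24/38 = 63.2% | 24/52 = 46.2% | −17.0 points |

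At 490 men per arm, the tester denominators would be 0.38 × 490 = 186 and 0.52 × 490 = 255. In the last row the intervention brings in extra testers who do not link, and a true null reads as harm. Keeping non-testers in the denominator as failures would preserve the headcount. The clock would still start on a different date for each man, and a linked man with no reported test would have no start date.

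**3. Three months against four.** For a self-test at month t, the part of the 3-month voucher period inside the outcome window is 3 − t months for a 3-month close. For a 4-month close it is 4 − t, capped at 3.

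| Self-test at | Inside a 3-month close | Inside a 4-month close |
|---|---|---|
| Month 1 | 2 of 3 (67%) | 3 of 3 (100%) |
| Month 2 | 1 of 3 (33%) | 2 of 3 (67%) |
| Month 3 | 0 | 1 of 3 (33%) |

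The documents do not say when men test or link, so the share of linkages between months 3 and 4 has to be assumed. Take self-tests spread evenly over the first 0.5, 1, 2 or 3 months. Take the delay to linkage as uniform over 3 months, or exponential with mean 0.5, 1 or 2 months truncated at 3. The share runs from 0.2% (tests within 0.5 month, mean delay 0.5) to 28% (tests over 3 months, uniform delay: 50.0% after month 3 less 22.2% after month 4). The choice of close may be trivial or material, and the plan cannot tell which.

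**The case against.** **The governing text is clear.** Protocol 1.3.3 and SAP section 26 agree on a fixed 3-month clock, and an analyst following them would make a valid intent-to-treat comparison. That clock is the same in both arms and independent of testing; leaving out later events is what a 3-month endpoint means. This stands as a defence of the 3-month horizon. It does not settle the definition: Table 2 is the protocol's statement of objectives and endpoints, the power section uses another close, and the SAP refers to Protocol version 4.0 while the protocol in hand is version 11.0. No rule of precedence is given.

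**Is the effect understated and power lost?** A reader might infer this, because a voucher used after month 3 produces linkage scored as failure. The documents do not support it. Shrinking 24% and 39% for late linkage would count the truncation twice. Protocol 1.2 allows about a fourth month. An equal proportional loss in both arms leaves the risk ratio unchanged, and the incentive may mainly bring linkage forward. A voucher valid to month 6 is itself an inference: section 8.5 states no printed expiry, and Table 1 does not mark redemption at 6 months.

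**Should the primary window move to 6 months?** A reader might infer this too. It would collide with the viral load taken 6 months after intervention start (Protocol 8.7) and with the retention denominator of men on ART or PrEP at 3 months (1.3.3). Section 8.7 also describes the abstraction cohorts as men taking ARVs and men starting PrEP, whereas linkage for HIV-negative men is evaluation for PrEP.

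**Conclusion.** The definition is wrong as written. One primary outcome has three windows, and the rule anchored on testing would break the intent-to-treat comparison if followed. That conclusion rests on the text alone. The figures for testers (63% against 75%, or 63% against 46% under a null) illustrate possible distortion, using the plan's Aim 1 and Aim 2 rates and the assumption that every linked man reported a test; they are not predictions. The difference between a 3- and a 4-month close is real but of unknown size, 0.2% to 28% of voucher-period linkages in the scenarios tried. The mismatch between the voucher period and the outcome window needs reconciling, but no bias or loss of power can be derived from it.

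**What to change.** 1. Define primary linkage once: documented linkage within 3 months of the date the network's promoter receives kits (intervention) or vouchers (control), for all randomised men, with men who have no documented linkage counted as not linked.
2. In Protocol Table 2, delete the clause tying the window to self-reported testing. Reword Ethical Considerations 3.1 so that linkage is not restricted to men reporting a self-test.
3. State once whether the extra month applies to the linkage event or only to data collection. Use that rule in Table 2, Protocol 1.2 and 1.3.3, and SAP sections 11, 15 and 26.
4. Reconcile the voucher period in section 8.5 with the redemption row of Table 1 and with the outcome window.
5. Report documented linkage to 6 months as a secondary or sensitivity outcome where the abstracted records cover it, and say which men they do not cover.

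Items 1 to 4 cost only wording, and neither the primary horizon nor the 24% planning rate changes. Item 5 may need abstraction beyond the two cohorts in section 8.7 if it is to include HIV-negative men evaluated for PrEP who did not start it. Settle the wording before linkage is tabulated by arm.
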